Error! Reference source not found. : Error! Reference source not found.	Simulation results updated as per the current recruitment rate of 0.27 patients/site/month.	Clarification
Throughout the SAP	Minor grammatical, formatting or spelling changes were made	Minor errors were noted

Amendment 3

Overall rationale for the Amendment: This amendment aims to align the Statistical Analysis Plan (SAP) to the protocol Amendment #2 issued on June 18, 2021 which introduced two interim analyses (IA) during the Part 1 of the study. The first IA (Part 1 IA1) will occur after all participants of Part 1 have completed at least Week 16 (or discontinued earlier) and the second one (Part 1 IA2) when all participants of Part 1 have completed at least Week 48 (or discontinued earlier). In addition, the unblinding of the sponsor, including the Sponsor Committee, for conducting and reviewing of results of the Part 1 IA1 and IA2 was introduced in this amendment.

During the conduct of Part 1 of this study, a higher than-expected proportion of participants (approximately 50% of 22 participants enrolled in Part 1 at the time of this amendment) experienced elevations of alanine aminotransferase (ALT) on treatment. Management of these acute elevations has been following the protocol defined criteria but some of the cases showed a prolonged pattern of ALT elevation for which no management criteria were provided in the protocol. To better characterize these observed ALT elevations and to protect participants from a potential risk, the Sponsor, after consultation with the Independent Data Monitoring Committee (IDMC), decided to implement the following changes:

1. Introduction of new treatment discontinuation criteria
2. Sponsor unblinding for review of antiviral activity parameters to interpret the ALT flares
3. Addition of two interim analyses (IA) of study Part 1 data

The first IA (Part 1 IA1) is planned after all participants of Part 1 have completed at least Week 16 (or discontinued earlier). This timepoint was chosen based on the observed pattern of ALT elevations occurring at or before treatment Week 16.

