Section 3.3.3 Rule to Start Part 2 of the Study or Determine Futility	Added the qualification “On-treatment” to the lab values used in the criteria defining antiviral activity.	Clarification
Section 4.6 Extent of Exposure	Updated derivation of durations of exposure.	Clarification and consistency with the wording used in Section 2.1.1 Analysis Phase
Section 5.1.1 Virology Data Handling Rules	LLOQ and imputed values updated for HDV RNA and HBV RNA.	Updates from external vendors on assay properties on RNA quantification.

Clarifications, Additions, Corrections		
Section Number and Name	Description of Change	Rationale
Section 5.5.1.1.4 JNJ-3989 Off-Treatment HDV RNA Relapses	Updated with additional definitions of off-treatment HDV RNA relapses	Clarification of approach to define different off-treatment HDV relapses based on HDV RNA value at End of Treatment visit.
Section 5.5.1.1.11 HBV Flares	Updated definition of virologic, biochemical and clinical flares by adding start and end dates for each type of flares.	Clarification of approach to identify distinct flare events over time.
Section 5.5.1.3.1 Time to Event Endpoints Based on Parameters Used in Key Secondary Endpoints	Analyses of time to event endpoints changed to overall during the study instead of by analysis phase.	Clarification.
Section 5.5.1.4 Additional Efficacy Endpoints Relative to The Actual Duration of JNJ-3989 Treatment and Section 5.6.1.3 Time to Event Endpoints	Added Table 5: Correspondence between timepoints for Arm 1 and Open Label timepoints for Arm 2 for the analysis based on actual duration of treatment exposure.	Alignment of time points to match the exposure to JNJ-3989+NA between the 2 arms, given the deferred active treatment design.
Section 5.6 Exploratory Endpoints	Added exploratory analyses for HDV RNA, HBV DNA and HBsAg	Added for accounting
Section 6.2.1 Definitions	Added imputation rules for laboratory data in the event of “<”, “>”, “≥” and “≤” being contained in the character result value.	Clarification
Section Error! Reference source not found. Error! Reference source not found.	Added definitions of HBV genetic and viral variations as well as parameters of interest with accompanying analyses.	Added for completeness
Section Error! Reference source not found. Error! Reference source not found.	Updated the calculation of the HBQOL total and subitems scores.	Correction

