3.2. Independent Flares Expert Panel

An independent flare expert panel (IFLEP) will be appointed. The IFLEP is composed of 3 independent medical experts with experience and expertise in HBV/HDV. The responsibilities of the IFLEP include: conduct regular review of all relevant and available individual participant blinded study data related to ALT flares; determine and adjudicate each ALT flare; and provide documentation of the final decision to IDMC. Adjudication review cycles will match IDMC schedule and will be set up ideally 2 weeks before IDMC.

In order to allow for an unbiased assessment, members of the committee will not serve as study investigators or as members of the IDMC. They will be unblinded to treatment assignment for all Part 1 participants from the time of Part1 IA1 and will remain blinded to the treatment assigned to

each participant of Part 2. Further details on the IFLEP process will be included in the IFLEP charter.

HBV Flares are defined in Section 5.5.1.1.11.

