5.5.1.1.11. HBV Flares

The criteria based on blood markers/lab tests for each of the flare types are defined as below.

a) HBV Virologic flare is defined as follows:

Derivation 1. This derivation of virologic flare will be assessed only for those participants who are off-treatment and had HBV DNA <LLOQ at the last observed point on-treatment.

The start date of a confirmed virologic flare is defined as the first date of two consecutive visits with HBV DNA > 200 IU/mL. The end date of the same confirmed virologic flare is defined as the first date when HBV DNA value returns to ≤ 200 IU/mL or the date of treatment restart (ie JNJ-3989 and/or NA), whichever comes first. Each virologic flare will be categorized based on the confirmed (ie two consecutive values) peak HBV DNA above any of the three thresholds within the start and end date of that flare as follows: 20,000 IU/mL 2,000 IU/mL and 200 IU/mL.

- 1 (Yes) = confirmed HBV DNA > peak threshold
- 0 (No) = at least one off-treatment HBV DNA measurement available and not meeting the criteria of confirmed HBV DNA > peak threshold.
- 2 (Not applicable) = no off-treatment HBV DNA quantitative measurements available.

Derivation 2. This derivation of virologic flare will be assessed only for those participants who are off-treatment and had HBV DNA \geq LLOQ at the last observed point on-treatment.

The start date of a confirmed virologic flare is defined as the first date of two consecutive visits with HBV DNA log₁₀ increase > 1 log₁₀ from EOT. The end date of the same confirmed virologic flare is defined as the first date when HBV DNA log₁₀ increase from EOT returns to \leq 1 log₁₀ or the date of treatment restart (ie JNJ-3989 and/or NA), whichever comes first. Each virologic flare will be categorized based on the confirmed (ie, two consecutive values) peak HBV DNA increase above any of the three thresholds within the start and end date of that flare as follows: 1 log₁₀, 2log₁₀, 3 log₁₀.

- (Yes) = confirmed HBV DNA increase from EOT > peak threshold
- 0 (No) = at least one off-treatment HBV DNA measurement available and not meeting the criteria of confirmed HBV DNA increase from EOT > peak threshold.
- 2 (Not applicable) = no off-treatment HBV DNA quantitative measurements available.

b) Off-treatment HBV biochemical flare is defined as follows:

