The start date of a confirmed off-treatment biochemical flare is defined as the first date of two consecutive visits with ALT and/or AST \geq 3x ULN and \geq 3x nadir (ie, lowest value observed up to the start of the flare). The end date of the same off-treatment biochemical flare is defined as the first date when there is a 50% reduction from the peak ALT and/or AST level or the date of treatment restart (ie JNJ-3989 and/or NA), whichever comes first.

- 1 (Yes) = confirmed ALT and/or AST \geq 3x ULN and \geq 3x nadir (ie, lowest value observed up to the start of the flare)
- 0 (No) = otherwise

c) On-treatment HBV biochemical flare is defined as follows:

The start date of a confirmed on-treatment biochemical flare is defined as the first date of two consecutive visits with ALT and/or AST \geq 3x ULN and \geq 3x nadir (ie, lowest value observed up to the start of the flare). The end date of the same on-treatment biochemical flare is defined as the first date when there is a 50% reduction from the peak ALT and/or AST level, regardless of stopping JNJ-3989 and/or NA.

- 1 (Yes) = confirmed ALT and/or AST \geq 3x ULN and \geq 3x nadir (ie, lowest value observed up to the start of the flare)
- 0 (No) = otherwise

d) HBV Clinical flare is defined as follows:

A HBV clinical flare occurs either when a HBV virologic flare and off-treatment HBV biochemical flare overlap in time or when a HBV biochemical flare starts within 4 weeks following the end of a HBV virologic flare.

The start date of a HBV clinical flare is defined as the minimum start date of the HBV virologic flare and HBV biochemical flare. The end date of a HBV clinical flare is defined as the maximum end date of the HBV virologic flare and HBV biochemical flare, ie, the later date between HBV DNA returns to ≤ 200 IU/mL (or $\leq 1 \log_{10}$) and 50% reduction from the peak ALT and/or AST level reached during the HBV biochemical flare.

- 1 (Yes) = confirmed HBV DNA $>$ peak threshold (for derivation 1 of virologic flare) or HBV DNA increase from end of treatment $>$ peak threshold (for derivation 2 of virologic flare) and confirmed ALT and/or AST $\geq 3x$ ULN and $\geq 3x$ nadir (ie, lowest value observed up to the start of the flare)
- 0 (No) = otherwise

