5.5.1.1.12. ALT/AST Elevations

ALT/AST elevation is defined as follows:

The start date of a confirmed ALT/AST elevation is defined as the first date of two consecutive visits with ALT and/or AST $\geq 3x$ ULN and $\geq 2x$ nadir (ie, lowest value observed up to the start of the flare). The end date of the same ALT/AST elevation is defined as the first date when ALT (and/or AST) $< 3x$ ULN or ALT (and/or AST) $< 2x$ nadir (ie, lowest value observed up to the start of the flare) whichever comes first.

- 1 (Yes) = confirmed ALT and/or AST $\geq 3x$ ULN and $\geq 2x$ nadir (ie, lowest value observed up to the start of the flare)
- 0 (No) = otherwise

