5.5.2.1.4. HBV Flares

The incidence rate will be calculated and summarized for each type of on-treatment or off-treatment flares (virologic, biochemical and clinical) separately, as well as the overall incidence of participants experiencing at least one flare, regardless of type. Additionally, for each participant the total number of flares the participant experienced will be counted by type. Such counts will be used to summarize the distribution of the total number of flares by type and by intervention arm.

For on-treatment biochemical flares, the incidence of flares causing treatment discontinuation will be summarized. Further, for off-treatment flares, the count and percentage of participants who experienced a flare followed by NA re-treatment will be summarized by flare type. Similarly, the incidence of flares followed by the achievement of HBsAg seroclearance (at any time) will be summarized by flare type. Flares that are associated with signs of liver decompensation will be provided in a listing.

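### The 50%-from-peak end rule can close a biochemical flare while its start criterion is still met, so a high, slowly recovering ALT/AST episode can be counted as two or three flares

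*SAP*

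**What the plan says.** **Start** (SAP 5.5.1.1.11 c): "The start date of a confirmed on-treatment biochemical flare is defined as the first date of two consecutive visits with ALT and/or AST" at least 3xULN and at least 3x nadir. Nadir is the lowest value up to the start of the flare. The off-treatment definition in b) starts the same way.

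**End:** on treatment, the "first date when there is a 50% reduction from the peak ALT and/or AST level, regardless of stopping JNJ-3989 and/or NA". Off treatment, the same 50% reduction or treatment restart, whichever comes first.

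**Use** (5.5.2.1.4): each participant's flares are counted by type. "Such counts will be used to summarize the distribution of the total number of flares by type and by intervention arm".

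**Purpose:** the Amendment 2 history gives the reason for adding flare start and end dates as "Clarification of approach to identify distinct flare events over time".

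**Neighbouring definitions:** for virologic flares (derivation 1), "The end date of the same confirmed virologic flare is defined as the first date when HBV DNA value returns to" 200 IU/mL or lower, which is the start limit. An ALT/AST elevation (5.5.1.1.12) ends when the value falls below 3xULN or below 2x nadir, again its own start limits.

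**The concern.** The start rule is a threshold and the end rule is a fraction of the peak, so the two do not exclude each other. After a high peak the enzyme can halve and still be above both start limits. The nadir for the next flare is still the low value from before the episode, so no new rise is needed: the next two qualifying visits on the way down satisfy the definition of another flare. The section has no merging, washout or nadir-reset rule.

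The count would then reflect peak height and slow recovery as well as repeat events. This matters here because ALT elevation is the main safety question of the study, and the Amendment 3 rationale reports that in Part 1 "some of the cases showed a prolonged pattern of ALT elevation". Flare dates also feed the clinical flare definition in 5.5.1.1.11 d).

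A second gap is that the end rule refers to the peak of ALT and/or AST without saying which enzyme must halve when both met the start criterion.

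**Working it through.** The SAP gives no figure for this point, so there is none to reproduce.

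**Inputs from the SAP.** ALT ULN is 43 U/L for males and 34 U/L for females (5.3.1). Visits are 4-weekly for most of the treatment period (Table 2). The start and end rules are those above.

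**Inputs that are assumptions.** All enzyme profiles, nadirs and the AST ULN.

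**Necessary condition.** Let P be the peak, U the ULN, N the nadir and x the value at the end date. The end rule gives x ≤ P/2. Meeting the start rule again needs x ≥ 3U and x ≥ 3N. Hence P ≥ 6U and P ≥ 6N. In U/L, 6xULN is 6 × 43 = 258 (male) and 6 × 34 = 204 (female).

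**This is not sufficient.** Two consecutive visits must still qualify. The text leaves two readings: (a) the visit that ends one flare may also start the next; (b) the next start is sought from the following visit.

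Take a smooth fall with half-life h weeks, 4-weekly visits from the peak and nadir no higher than 1xULN. The value t weeks after the peak is P × 2^(−t/h). A second flare needs this to be at least 3U at the later of the two qualifying visits, so the smallest peak is 3 × 2^(t/h) in multiples of ULN:

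| h (weeks) | first halved visit | (a) smallest peak | (b) smallest peak |
|---|---|---|---|
| 4 | +4 | 3 × 2^(8/4) = 12.0 | 3 × 2^(12/4) = 24.0 |
| 6 | +8 | 3 × 2^(12/6) = 12.0 | 3 × 2^(16/6) = 19.0 |
| 8 | +8 | 3 × 2^(12/8) = 8.5 | 3 × 2^(16/8) = 12.0 |
| 12 | +12 | 3 × 2^(16/12) = 7.6 | 3 × 2^(20/12) = 9.5 |

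**Counts over a grid** of peaks 5, 6, 8, 10, 15, 20 and 30xULN with these four half-lives (28 cells). Under (b), 10 cells give more than one flare, all at 10xULN or above. Under (a), 15 cells do, from 8xULN. The largest count is 3. If a flare ended only on loss of the start criterion, every cell would give 1.

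**Worked profile.** Male, nadir 43, so both start limits are 129. ALT is 300, 800, 400, 350, 300, 140, 80 at Weeks 8, 12, …, 32.
- Flare 1: starts Week 8; ends Week 16 (400 ≤ 800/2).
- Flare 2 under (a): starts Week 16 (400 and 350 ≥ 129); ends Week 28 (140 ≤ 400/2).
- Flare 2 under (b): starts Week 20 (350 and 300 ≥ 129); ends Week 28 (140 ≤ 350/2).
- ALT never fell below 129 between Weeks 8 and 28. Nadirs of 30 and 50 also give 2 flares.

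A longer fall after two low visits (300, 800, 700, 390, 350, 300, 180, 140, 100, 60, 40; nadir 40) gives 3 flares under (a) and 2 under (b).

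**Two enzymes.** Assume AST ULN 40, ALT nadir 40 and AST nadir 35, with visits from Week 8. ALT is 300, 400, 380, 330, 260, 190, 90; AST is 250, 320, 150, 90, 60, 50, 40. AST halves at Week 16 (150 ≤ 160) while ALT (380, 330) still qualifies. If the first enzyme to halve closes the flare, there are 2 flares; if both must halve, there is 1, ending at Week 28 (190 ≤ 200).

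**What is unaffected.** The end rule acts only after a first flare has been found, so whether a participant has at least one flare is the same under every reading.

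**The case against.** - **The text does not order a new flare on a falling value.** It bounds one flare and is silent on re-entry, and a programmer mindful of the stated purpose might decline to open a second. That is fair, but the rules taken literally do open it, and two programmers could report different counts. Reading the definition as one flare per participant would make the planned count pointless.
- **Prolonged courses have their own endpoint.** For a single enzyme, an ALT/AST elevation has wider entry limits and ends on loss of its criterion, so a continuous episode appears there once. ALT over time is plotted too. This limits the harm but does not correct the flare table.
- **An expert panel reviews flares.** Under 3.2 it is to "determine and adjudicate each ALT flare; and provide documentation of the final decision to IDMC". Section 5.5.2.1.4 does not say that the count uses those decisions, and 3.2 refers back to 5.5.1.1.11 for the definition.
- **Ending on recovery from peak is defensible, and an exit rule alone would do harm.** With ALT 300, 800, 300, 200, 600, 900, 400, 100 (male, nadir 43), the current rules count 2 flares. Requiring exit from the start range would merge a real second rise or, with the 50% end date kept, leave it outside any flare. This stands, and it shapes the fix.
- **The contrast with 5.5.1.1.12 is not complete.** That section has the same ALT and/or AST ambiguity: in the two-enzyme example AST is 90 at Week 20, below 3 × 40 = 120, while ALT (330, 260) still qualifies. The contrast holds for one enzyme only.

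A reader might infer that every peak above 6xULN is double-counted, or that Part 1 counts were inflated. The documents support neither: 6xULN is only a necessary condition, and no peaks are reported.

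**Conclusion.** Wrong as written, minor severity. The start and end rules in 5.5.1.1.11 b) and c) can split one continuous episode into two or three flares, contrary to the stated aim of identifying distinct events. It takes a peak of at least 6xULN and 6x nadir and, in the assumed profiles, about 10xULN or more with slow recovery (from about 7.6xULN at a 12-week half-life if one visit may both end and start a flare).

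The effect is confined to the descriptive flare count by type and arm and to flare dates. A reader might infer that flare incidence or an efficacy conclusion is distorted; the proportion with at least one flare does not change, and no primary or key secondary endpoint uses these definitions. The size rests on assumed profiles, and the real frequency is unknown.

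**What to change.** In 5.5.1.1.11 b) and c), keep the 50% end date and add a re-entry rule. After a flare ends, a new one may start only if the enzyme:
- has first fallen below 3xULN or below 3x nadir; or
- meets at least 3xULN and at least 3x the lowest value observed since the previous flare's peak (nadir reset).

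A value that is still falling is itself the post-peak low, so it cannot open a new flare. The worked profile, the longer fall and all 28 grid cells then give 1 flare. In the second-rise example the post-peak low is 200; 600 and 900 are both at least 3 × 200 = 600, so it still counts 2.

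Apply the rules per enzyme, with the later enzyme setting the end date when both met the start criterion. Make the same ALT/AST clarification in 5.5.1.1.12.

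Cost: a few sentences and one derivation change on data already collected. Downside: a second rise smaller than 3x the post-peak low that begins before the enzyme leaves the flare range is merged into the first flare. The planned ALT spaghetti plots (5.5.2.2) would still show it.

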5.5.1.1.12. ALT/AST Elevations

ALT/AST elevation is defined as follows:

The start date of a confirmed ALT/AST elevation is defined as the first date of two consecutive visits with ALT and/or AST $\geq 3x$ ULN and $\geq 2x$ nadir (ie, lowest value observed up to the start of the flare). The end date of the same ALT/AST elevation is defined as the first date when ALT (and/or AST) $< 3x$ ULN or ALT (and/or AST) $< 2x$ nadir (ie, lowest value observed up to the start of the flare) whichever comes first.

- 1 (Yes) = confirmed ALT and/or AST $\geq 3x$ ULN and $\geq 2x$ nadir (ie, lowest value observed up to the start of the flare)
- 0 (No) = otherwise

5.5.1.1.13. Liver Stiffness Measurement

The proportion of participants with the following LSM changes from baseline (both in terms of reductions and increases) will be evaluated over time:

- ≥ 1 kPa
- ≥ 2 kPa
- ≥ 4 kPa
- ≥ 6 kPa

Only participants from sites with available VCTE (Fibroscan) will be included in the analysis. Within these participants, missing LSM (in kPa) at a specific timepoint will be considered as non-responders for that timepoint.

5.5.1.2. Values and Changes Over Time

Change from baseline is defined as the value at a given time point minus the baseline value.

Actual values (original unit and \log_{10} transformed values, where applicable) and changes from baseline (\log_{10} transformed values, where applicable) will be derived for the following parameters:

HDV virology:

- HDV RNA (original unit and \log_{10} transformed values)

Liver inflammation

- ALT

Liver Fibrosis:

- Liver stiffness measurement assessed by vibration-controlled transient elastography (FibroScan)

HBV virology and serology:

- HBsAg (original unit and \log_{10} transformed values)
- HBeAg (only for participants HBeAg-positive at screening; original unit and \log_{10} transformed values)
- HBV RNA (original unit and \log_{10} transformed values)
- HBV DNA (original unit and \log_{10} transformed values)

5.5.1.3. Time to Event Endpoints

5.5.1.3.1. Time to Event Endpoints Based on Parameters Used in Key Secondary Endpoints

All time to event endpoints will analyzed throughout the entire study (and not by study phase) using DB day 1 as reference timepoint by study part.

5.5.1.3.1.1. Time to HDV RNA $\geq 2 \log_{10}$ IU/mL Decline or HDV RNA TND or <LLOQ

Time to reach HDV RNA $\geq 2 \log_{10}$ IU/mL decline or HDV RNA TND is defined as the number of days between the date of first study intervention intake and the date of the first occurrence of HDV RNA $\geq 2 \log_{10}$ IU/mL decline or HDV RNA TND, whichever event is first (i.e. \min [the date of the first HDV RNA $\geq 2 \log_{10}$ IU/mL decline, date of the first time HDV RNA is TND] – the date of first study intervention intake + 1). The participants who withdrew early from the study before achieving such event, or who did not achieve it at the time of the cut-off date for the analysis will

be censored at the last available HDV RNA assessment during the study or the cut-off date, whichever comes first.

5.5.1.3.1.2. Time to HDV RNA $\geq 2 \log_{10}$ IU/mL Decline

The same derivation and censoring rules as in Section 5.5.1.3.1.1 apply for the time to reach HDV RNA decline $\geq 2 \log_{10}$ IU/mL, which will be calculated using the date of first HDV RNA decline $\geq 2 \log_{10}$ IU/mL.

5.5.1.3.1.3. Time to HDV RNA TND or <LLOQ

The same derivation and censoring rules as in Section 5.5.1.3.1.1 apply for the time to reach HDV RNA TND and time to reach HDV RNA < LLOQ, which will be calculated using the date of first HDV RNA TND and date of first HDV RNA < LLOQ respectively.

5.5.1.3.1.4. Time to Normal ALT Levels

The same derivation and censoring rules as in Section 5.5.1.3.1.1 apply for the time to reach normal ALT (i.e. ALT value \leq ULN), which will be calculated using the first date of normal ALT value.

5.5.1.3.1.5. Time to HBsAg Thresholds

The following thresholds will be evaluated:

- HBsAg < LLOQ (i.e seroclearance)
- HBsAg < 1 IU/mL
- HBsAg < 10 IU/mL
- HBsAg < 100 IU/mL
- HBsAg decline $\geq 2 \log_{10}$ IU/mL

The same derivation and censoring rules as in Section 5.5.1.3.1.1 apply for the time to reach HBsAg thresholds, which will be calculated using the date of first occurrence of the given HBsAg threshold.

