1.2. Trial Design

Prior Protocol Amendment #4 the study was planned to include 2 parts, Part 1 (approximately N=20) with proof of concept objectives and Part 2 (approximately N=145) with confirmatory objectives. As of Protocol Amendment #4, Part 2 sample size was reduced to 30 participants which triggered modifications of objectives of Part 2 from confirmatory to exploratory.

Part 2 of the study will only be initiated once the antiviral activity criteria in Part 1 have been met and after evaluation of the results of the first IA during the double-blind phase of Part 1. Cirrhotic participants will be excluded from participation in Part 2 of the study.

Each part includes 3 phases: a 4-week screening phase (may be extended up to a maximum of 6 weeks), 144-weeks study intervention phase (Arm 1) and 148-weeks study intervention phase (Arm 2), 48-week follow-up phase. The first 52 weeks of the intervention phase are double-blind followed by 96 weeks of open-label (OL) treatment.

In each part the participants will be randomized in a 4:1 ratio to Arms 1:2.

- Arm 1: 100 mg JNJ-3989 (subcutaneous [SC] injection every 4 weeks [Q4W]) + NA qd for 144 weeks;
- Arm 2: placebo for JNJ-3989 (SC injection Q4W) + NA qd for 52 weeks, followed by 100 mg JNJ-3989 (SC injection Q4W) + NA qd for 96 weeks (control deferred active treatment arm).

Randomization will be stratified by presence of compensated cirrhosis at screening (yes or no) (Part 1 only), HDV RNA testing laboratory location (China versus outside China) (all sites in China will utilize the laboratory testing in China and all sites in other countries will utilize the laboratory outside of China), and HBeAg status at screening (positive versus negative).

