5.5.1.4. Additional Efficacy Endpoints Relative to The Actual Duration of JNJ-3989 Treatment

This section intends to evaluate some selected efficacy endpoints over time conditional upon the same treatment duration with JNJ-3989 across the 2 arms based on Part 2 data. For example, DB

Week 24 for Arm 1 corresponds to Week 76 for Arm 2 (Week 52+24, See [Table 2](#)), as participants in Arm 2 start treatment with JNJ-3989 at Week 52 when they switch over to the active regimen. For each DB Week X for Arm 1 data, the corresponding Week 52+X for Arm 2 data will be considered, as described in [Table 5](#):

Table 5: Correspondence between timepoints for Arm 1 and Open Label timepoints for Arm 2

Analysis Time point for Arm 1 (label)	Matching Analysis OL Timepoint for Arm 2 (label)
Baseline	Week 52
Week 2	Week 54
Week 4	Week 56
Week 8	Week 60
Week 12	Week 64
Week 16	Week 68
Week 20	Week 72
Week 24	Week 76
Week 28	Week 80
Week 32	Week 84
Week 36	Week 88
Week 40	Week 92
Week 44	Week 96
Week 48	Week 100
Week 52	Week 104
Week 56	Week 108
Week 60	Week 112
Week 64	Week 116
Week 68	Week 120
Week 72	Week 124
Week 76	Week 128
Week 80	Week 132
Week 84	Week 136
Week 88	Week 140
Week 92	Week 144
Week 96	EOT (only for OL completers)

When applicable, the reference timepoint (RT) for those analyses will be baseline (DB Day 1) for Arm 1 and Week 52 for Arm 2.

The following endpoints will be presented for those time points during the open-label phase in Arm 2 that match the treatment duration in Arm 1 during the double-blind phase, because of the deferred active trial design, as per [Table 5](#).

The selected endpoints are:

- Proportion of participants with HDV RNA $\geq 2 \log_{10}$ IU/mL decline from RT or HDV RNA TND in combination with normal ALT
- Proportion of participants with HDV RNA $\geq 2 \log_{10}$ IU/mL decline from RT or HDV RNA $<$ LLOQ in combination with normal ALT

- Proportion of participants with HDV RNA $\geq 2 \log_{10}$ IU/mL decline from RT or HDV RNA TND
- Proportion of participants with HDV RNA TND
- Proportion of participants with HDV RNA <LLOQ
- Proportion of participants with normal ALT
- Proportion of participants with LSM reduction ≥ 2 kPa from RT
- Proportion of participants with HBsAg seroclearance i.e. with HBsAg < LLOQ, with HBsAg < 1 IU/mL and < 10 IU/mL
- Change from RT in HDV RNA
- Change from RT in ALT
- Change from RT in HBsAg
- Change from RT in LSM

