5.5.2.3. Time to Event Endpoints

The Kaplan-Meier method will be used to estimate and plot the cumulative incidence by each intervention arm. The log-rank test will be performed to compare the intervention arms. The median time with 95% CI will be estimated using Kaplan-Meier method. This analysis method will apply to all time-to-events variables defined in Section 5.5.1.3.

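### Whole-study log-rank comparisons count Arm 2 responses on JNJ-3989 after Week 52 as control-arm events, and conflict with the plan's bar on formal testing of open-label and follow-up data

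*SAP*

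**What the plan says.** SAP Section 5.5.1.3.1 covers time to HDV RNA decline, TND or <LLOQ, time to normal ALT, and time to HBsAg thresholds. It sets the period and origin: "All time to event endpoints will analyzed throughout the entire study (and not by study phase) using DB day 1 as reference timepoint". Participants without the event are to "be censored at the last available HDV RNA assessment during the study or the cut-off date, whichever comes first".

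Section 5.5.2.3 plans Kaplan-Meier curves and medians by arm and adds: "The log-rank test will be performed to compare the intervention arms". On scope it says: "This analysis method will apply to all time-to-events variables defined in Section 5.5.1.3". The exploratory endpoints in Section 5.6.1.3 reuse the same derivation and censoring, and Section 5.6.2.3 applies the same log-rank test to them.

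Section 1.2 gives the Arm 2 regimen: "placebo for JNJ-3989 (SC injection Q4W) + NA qd for 52 weeks, followed by 100 mg JNJ-3989". It also gives the length of each period: "The first 52 weeks of the intervention phase are double-blind followed by 96 weeks of open-label (OL) treatment". Section 5.5.1.4 confirms the timing: "participants in Arm 2 start treatment with JNJ-3989 at Week 52 when they switch over to the active regimen". Section 1.5 makes one exception: Part 2 placebo participants with HBsAg above 10,000 IU/mL at screening or baseline do not receive open-label JNJ-3989.

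**The concern.** A participant randomised to Arm 2 who first responds at, say, Week 80 after 28 weeks on JNJ-3989 enters the log-rank test as a control-arm event. No text censors at the switch, restricts these tests to the double-blind phase, or treats exposure as time-varying.

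A reader who sees a log-rank p-value or a median beyond Week 52 by arm will take it as active against placebo. It is a comparison of starting JNJ-3989 now with starting it a year later, with some Arm 2 participants never starting. The issue is not confined to the final analysis: the primary analysis is cut when the last participant reaches Week 48, and participants enrolled earlier may by then be past Week 52.

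**Working it through.** **1. The passages side by side**

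| Place in the SAP | Rule |
|---|---|
| 5.5.1.3.1, 5.5.2.3 | Log-rank between arms, whole study, from DB Day 1 |
| 5 (Efficacy, opening text) | Open-label and follow-up efficacy descriptive only, no formal tests |
| 5.5.2.2.1.2, and by reference 5.5.2.2.2 and 5.5.2.2.3.2 | MMRM arm comparisons limited to the double-blind phase |
| 5.5.1.4 | Arm 2 realigned to its Week 52 start, but only for proportions and changes |

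The first row conflicts with the second and departs from the third. The fourth does not extend to any time-to-event endpoint.

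**2. Inputs for an illustration**

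The SAP gives no event-time rates. The stand-ins are the Week 48 primary-endpoint rates: 4% for placebo (Section 1.4) and 30% for Arm 1 (Attachment 3). They are the rates behind the only stated design figure, power above 90% with N=130 (Section 1.4). At 104:26 and one-sided 0.025, the normal approximation gives 89.6% with pooled variance and 99.3% unpooled, so that figure is essentially reproduced. Part 2 as run has 30 participants, about 24:6 at 4:1.

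Further assumptions: constant hazards, no dropout, and either all or half of Arm 2 taking the Arm 1 hazard after Week 52. The number who roll over is not stated.

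**3. Share of Arm 2 events after Week 52 (to Week 148)**

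- Hazards per week: Arm 1, −ln(0.70)/48 = 0.00743; control, −ln(0.96)/48 = 0.00085.
- Event by Week 52 in Arm 2: 1 − exp(−0.00085 × 52) = 0.043, or 6 × 0.043 = 0.26 events.
- Event in Weeks 52–148 if switched: 0.957 × [1 − exp(−0.00743 × 96)] = 0.488, or 2.93 events.
- Event in Weeks 52–148 if not switched: 0.957 × [1 − exp(−0.00085 × 96)] = 0.075.
- All switching: 0.488/(0.043 + 0.488) = 92% of Arm 2 events come after Week 52, all on JNJ-3989.
- Half switching: (0.244 + 0.0375)/(0.043 + 0.2815) = 87% come after Week 52. The part on JNJ-3989 is 0.244/0.3245 = 75%.

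**4. Simulated log-rank at 24:6, events read at 4-weekly visits**

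Z = (O − E)/√V and one-step hazard ratio = exp[(O − E)/V], with O − E and V from the log-rank test. Entries are the median ratio and mean Z.

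| Arm 2 switching | Ratio to Week 52 | Ratio to Week 144 | Z to Week 52 | Z to Week 144 |
|---|---|---|---|---|
| All | 3.7 | 1.6 | 1.3 | 0.8 |
| Half | 3.7 | 2.3 | 1.3 | 1.5 |
| None | 3.7 | 3.9 | 1.3 | 2.1 |

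The true ratio under these hazards is 0.00743/0.00085 = 8.7. The one-step estimate compresses large ratios, so the columns should be read against each other. The last row shows that without switching the ratio does not fall.

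In a variant where a fixed fraction responds within 4–48 weeks of starting JNJ-3989, the whole-study ratio is 1.2 (all switching) or 1.8 (half), with Z of 0.2 or 0.7. Part of that fall is not due to switching: with none switching the ratio is already 2.9.

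**The case against.** The whole-study comparison is deliberate. The SAP names Arm 2 a deferred-treatment control. The objectives above these endpoints in Section 1.1 cover the intervention and follow-up periods and do not name NA alone. Comparing randomised arms throughout is a legitimate immediate-versus-deferred contrast. This stands, but the plan nowhere labels the result that way, and Section 5 still bars the test.

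A reader might infer that the comparison with NA alone is lost. It is not. That is the primary objective, and the Week 48 proportions and the double-blind MMRMs address it. Kaplan-Meier estimates up to Week 52 are also intact, and time to off-treatment relapse (Section 5.5.1.3.2.1) counts from end of treatment.

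A reader might also infer that the test is always pushed towards no difference. With half switching and constant hazards, Z rises from 1.3 to 1.5 because more events are counted. Nor is it a fact that most Arm 2 events occur on drug, since that depends on the unstated number who roll over.

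Finally, the plan estimates no hazard ratio for these endpoints, so the ratios in the working are a yardstick and not a planned output. That is correct.

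**Conclusion.** The point holds. As written, the between-arm log-rank tests, and any median beyond Week 52, mix on-drug Arm 2 responses into the control arm and contradict Section 5. Under the stated assumptions the one-step ratio falls from about 3.7 to about 1.6 with full roll-over and to about 2.3 with half. The share of Arm 2 events falling after Week 52 is about 92% or 87%. The effect measure is diluted in each switching scenario examined; the test statistic is not always weakened. These sizes rest on stand-in rates from a different endpoint and on assumed roll-over.

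It is tempting to call this a must-fix flaw, but the documents do not support that. These are other secondary and exploratory analyses, without multiplicity adjustment, in a study that Section 1.3 now calls descriptive. It should be fixed before the tables are produced.

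**What to change.** In Section 5.5.2.3, and by reference Section 5.6.2.3, state that between-arm log-rank tests and medians for the endpoints counted from DB Day 1 censor both arms at the end of the double-blind phase as defined in Table 1. Show whole-study curves without a test, either labelled immediate versus deferred treatment or drawn from each arm's first JNJ-3989 injection.

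Two details need wording. Table 1 ends the phase the day before the Week 52 study-agent intake, which placebo participants who do not roll over will not have, so a projected Week 52 date is needed for them. For early discontinuers Table 1 ends the phase at the earlier of withdrawal and study-agent discontinuation; the SAP should say whether censoring there is intended.

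The cost is a few sentences and one censoring variable. The downside is power: only about 0.2–0.3 Arm 2 events are expected in Part 2 by Week 52 at these rates, and the restricted test rejects only about 4–5% of the time at the two-sided 5% level. It answers the right question but will rarely be decisive.
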